We will identify a prevalent cohort of patients aged \geq 18 years old with a diagnosis of T2DM, included in the CPRD between 1 Jan 2011 and 31 Dec 2019. We will exclude those aged <18 years who are much more likely to have type 1 DM. We will include only patients who intensify treatment with a second oral treatment after a previous period of metformin monotherapy, the recommended drug for initiation. We will define 'baseline' as the date of the first prescription for second-line treatment. To help ensure that the study includes only those patients who have received metformin prior to second-line treatment we will includeonly patients registered at a General Practitioner (GP), for at least twelve months prior to second-line treatment. We will exclude patients who start more than one new antidiabetic treatment on the same day, those who discontinue metformin prior to 'baseline', and those without the HES linkage required for information on long-term outcomes.

[figure not shown]
Comparators and second-line treatment cohorts

We will include patients prescribed the three most common classes of drugs for second-line treatment. In our 2016 CPRD pilot data, the most frequently prescribed drug classes for second-line treatment were DPP4i (41.4 %), SU (35.4%) and SGLT2i (15.4%), which have all been recommended by NICE and SIGN. We will group patients according to which class of therapy they started at second-line treatment. We will exclude other comparators that were used infrequently in the pilot data, namely thiazolidinedione (TZDs, 2.5%), and injectable insulin (2.7%), and Glucogen-like peptide-1 agonists, (GLP-1,1.8%), because patients tend to prefer non-injectable therapies when offered the choice.

We will define a *'long-term outcomes cohort'* as eligible patients who initiated second-line treatment any time 1.1.2011-31.12.2019, providing the long-term follow-up of up to 7.6 years required for the RAPIDS- UK model. Our feasibility count suggest that this cohort will contain approximately 38,000, 29,000 and 8,000 patients who had second-line treatment with SU, DPP4i and SGLT2i respectively which is the pertinent sample for objective 5. We will also define a subsample of patients for the *'comparative effectiveness cohort'* (objective 2) limited to patients prescribed second-line treatment between 1.1.2016-31.12.2019 (SU=6,000; DPP4i, 13,000 and SGLT2i=6,700).

Fig. 2. Proportion of patients receiving each treatment in CPRD pilot data.

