Secondary outcomes will include: change in HbA1c at 2-years, and change in BMI, SBP, and eGFR all at 1and 2-years. We also reported the time to the following first events before 2-years follow-up: (a) a 40% decline in eGFR from baseline, which could be a marker for the rarer end-stage kidney disease (ESKD) outcome,²² (b) a major adverse kidney event (MAKE), a composite outcome for the earliest of a decline in eGFR from baseline of 40%, ESKD, and all-cause mortality,(c) heart failure hospitalisation, (d) 3-point major adverse cardiovascular event (MACE), a composite outcome for the earliest of myocardial infarction, stroke, and CVD death, and (e) all-cause mortality. We also reported time to myocardial infarction and stroke individually.

Sample size calculation

The study will include approximately 25,700 (SU=6000, DPPi4=13,000, SGLT2i=6,700) patients who meet the eligibility criteria. The FDA recommends that an average between-treatment difference in the HbA1c change from baseline of 0.4% (e.g. from 8.0% to 7.6%) is of clinical significance⁴². The assumed standard deviation of 2.4 is taken from a previous study of patients with T2DM recruited from CPRD⁴³. We follow methodological recommendations for sample size calculations with IV designs, by assuming a 'base case' level of non-compliance of 10%, but also consider scenarios with alternative levels¹. We require 90% power at the 5% (2-sided) level of statistical significance. We follow methodological recommendations for sample size calculations with IV designs, it will not perfectly predict the treatment received, and so we assume the 'base case' compliance (the proportion of patients in who actually receive the treatment predicted by the IV) is 80%, but also consider scenarios where the V is weaker (70% compliance) and stronger (90%). Table 1 shows the requisite sample sizes for the two treatment groups projected to have fewest patients (SU and SGLT2i). The anticipated sample sizes will be more than sufficient across these scenarios for detecting whether the overall estimates of treatment effectiveness are statistically significant.

With the projected sample sizes, we can also report estimates of treatment effectiveness with sufficient precision for major subgroups of prime interest, for example according to established CVD (or not), and broad categories by age, and levels of baseline HbA1c, and eGFR.

	Level of	compliance (IV strengt	th)		
70%			80)%	909	%

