Effect size: between-treatment difference in mean HbA1c reduction baseline to 12 months	SU	SGLT2i	SU	SGLT2i	SU	SGLT2i
0.3	3416	1464	2615	1121	2066	886
0.4	1921	823	1471	630	1162	498
0.5	1230	527	941	403	744	319

Table 1: Required sample size (N) for the IV design according to instrument strength (level of compliance) and magnitude of effect size at 90% power and 2.5% (2-sided) level of statistical significance

Analysis

An instrumental variable (IV) analysis will address confounding by indication. The instrumental variable approach taken will be the two-stage residual inclusion (2SRI) method.²³ This approach will enable us to report comparative effectiveness across the full study populations of interest, that is, to report average treatment effects, while addressing the risk of bias from unmeasured confounding. The first stage models will estimate the probabilities for each person to be prescribed each treatment given their baseline covariates and their CCG's tendency to prescribe (TTP) that treatment. The second-stage outcome models will include generalised residuals from the first stage (propensity score) models. The outcome models will be estimated by ordinary least squares (OLS) for continuous outcomes (e.g. 1-year HbA1c), and Cox proportional hazards models for time-to-event outcomes.⁴⁵ All standard errors will be calculated with non-parametric bootstrapping, and will account for clustering of individuals within practices, and within- individual correlation introduced by repeated measures of outcomes.

Sensitivity analyses

We will undertake sensitivity analyses to consider data issues, for example by applying alternative exclusion criteria for when there is doubt about the clinical coding of T2DM⁴⁶ or the second-line treatment regimen. We will consider different assumptions about missingness patterns, for example by undertaking complete records analysis⁴⁷. We will examine the robustness of the findings to alternative statistical models including those that use traditional IV designs and risk-adjustment.

Output

We will provide estimates of the comparative effectiveness of second-line treatments with SUs vs DPP4is vs SGLT2is.

Objective 3: To examine heterogeneity in the comparative effectiveness of DPP4i versus SU

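### Table 1 sizes SU against SGLT2i at an unstated 7:3 ratio, while the Objective 2 cohort is projected at 6,000 to 6,700, so its pairs are not the requirement for this cohort

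*Protocol*

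**What the plan says.** Under Objective 2, Sample size calculation, the protocol projects the cohort: "The study will include approximately 25,700 (SU=6000, DPPi4=13,000, SGLT2i=6,700) patients who meet the eligibility criteria". The section on comparators and second-line treatment cohorts gives the same counts for the comparative effectiveness cohort: "SU=6,000; DPP4i, 13,000 and SGLT2i=6,700".

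The sizing assumptions are a "average between-treatment difference in the HbA1c change from baseline of 0.4" percentage points, with 0.3 and 0.5 as alternatives, and an SD given as follows: "The assumed standard deviation of 2.4 is taken from a previous study of patients with T2DM recruited from CPRD". Compliance with the instrument is taken as 80%, with 70% and 90% as scenarios. On error rates the text says "We require 90% power at the 5% (2-sided) level of statistical significance"; the caption of Table 1 also says 90% power but gives 2.5% two-sided.

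The table is introduced with "Table 1 shows the requisite sample sizes for the two treatment groups projected to have fewest patients (SU and SGLT2i"). Its middle row reads "0.4 1921 823 1471 630 1162 498". Neither the text nor the caption states an allocation ratio. The section concludes that the expected numbers comfortably exceed the requirement in all scenarios. It then says that the projected numbers also allow adequate precision in major subgroups, such as established CVD and broad bands of age, baseline HbA1c and eGFR.

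**The concern.** A required sample size for two unequal groups depends on the ratio between them. Table 1 asks for more than twice as many SU as SGLT2i patients in every cell, but the cohort it is meant to size has slightly more SGLT2i than SU patients. The table therefore answers the sizing question for a different mix of patients.

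What is at stake is how the table can be used. The overall comparison has patients to spare. The next claim in the section concerns subgroups, and Objective 4 goes on to study effect heterogeneity for all three drugs. There a reader needs to know how small a subgroup may be, and the two columns of Table 1 give very different answers, neither of them right for the projected mix.

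**Working it through.** **Inputs, all from the protocol:** SD 2.4; difference d = 0.3, 0.4 or 0.5; compliance c = 0.7, 0.8 or 0.9; projected counts 6,000 SU and 6,700 SGLT2i; 90% power with 5% two-sided (text) or 2.5% two-sided (caption).

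**Formula** (normal approximation for two means, difference diluted to c × d, r = SU/SGLT2i):

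n_SU = (2.4/(c·d))² × (z_α + z_β)² × (1 + r), and n_SGLT2i = (2.4/(c·d))² × (z_α + z_β)² × (1 + 1/r).

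**1. The ratio in the table.** 3416/1464, 2615/1121, 2066/886, 1921/823, 1471/630, 1162/498, 1230/527, 941/403 and 744/319 all lie between 2.332 and 2.335, that is 7:3. The projected ratio is 6,000/6,700 = 0.896.

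**2. Reproducing the table.** With r = 7/3, 80% power and 5% two-sided (z sum 1.960 + 0.842), all nine cells come out within 2 patients. For d = 0.4 the results are 1923/824, 1472/631 and 1163/499, against 1921/823, 1471/630 and 1162/498 printed. At 90% power no cell is reproduced at either alpha. Directly, for the 0.4/80% cell:

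Φ(0.32/(2.4·√(1/1471 + 1/630)) − 1.96) = 0.80.

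**3. Changing only the ratio.** Alpha, power, SD, effect and compliance cancel, so the ratio error is the same in every cell:

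- SU, printed over required: (1 + 7/3)/(1 + 0.896) = 1.76, about 76% too high.
- SGLT2i, printed over required: (1 + 3/7)/(1 + 1/0.896) = 0.67, about 33% too low.

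**4. Required numbers at 6,000:6,700, d = 0.4** (SU/SGLT2i, rounded up):

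| Compliance | Printed | 80% power, 5% | 90% power, 5% | 90% power, 2.5% |
|---|---|---|---|---|
| 70% | 1921/823 | 1094/1221 | 1464/1635 | 1729/1931 |
| 80% | 1471/630 | 837/935 | 1121/1252 | 1324/1478 |
| 90% | 1162/498 | 662/739 | 886/989 | 1046/1168 |

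Before rounding up, the 80% row is about 1,120 + 1,251 at 90%/5% and about 1,323 + 1,478 at 90%/2.5%. Against 90%/5% the printed SU numbers are about 31% too high and the SGLT2i numbers about 50% too low. Against 90%/2.5% the figures are about 11% and 57%. These last two pairs combine the ratio error with the power error.

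**5. Smallest subgroup, as a share of the cohort, d = 0.4 and c = 0.8** (assuming the subgroup has the cohort's SU:SGLT2i ratio):

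- SGLT2i column alone: 630/6,700 = 9%.
- SU column alone: 1,471/6,000 = 25%.
- Correct ratio, 80% power and 5%: 837/6,000 = 14%.
- Correct ratio, 90% power and 5%: 1,120/6,000 = 19%.

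In the hardest cell (0.3, 70%) the same four shares are 1,464/6,700 = 22%, 3,416/6,000 = 57%, 1,944/6,000 = 32% and 2,602/6,000 = 43%.

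**6. Power of such subgroups.**

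- With 630 SGLT2i patients and the matching 630 × 0.896 = 564 SU patients: Φ(0.32/(2.4·√(1/630 + 1/564)) − 1.96) = 0.63.
- With 1,471 SU patients and the matching 1,471/0.896 ≈ 1,643 SGLT2i patients: 96% at 5% two-sided and 93% at 2.5% two-sided.

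**7. Full cohort, hardest cell.** Effective difference 0.3 × 0.7 = 0.21: Φ(0.21/(2.4·√(1/6000 + 1/6700)) − 1.96) = 0.998. At 2.5% two-sided it is 0.996.

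**The case against.** The best defence is that a requirement for two groups is a pair, and each printed pair is a correct solution at its own ratio. It would be too strong to infer that every number in the table is simply miscalculated. Each pair delivers 80% power at 5% two-sided for a 7:3 split. This stands: the fault is that the ratio is unstated and is not the cohort's.

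A second tempting inference is that the plan leads to underpowered subgroups. The documents do not support that. The 63% power arises only for someone who meets the SGLT2i figure and ignores the SU figure beside it, and the protocol does not invite that reading. Someone who demands both numbers is bound by the SU column and ends with 96% power at 5% two-sided (93% at 2.5%), more than the stated 90%. Used that way, the table asks for larger subgroups than necessary. The subgroup sentence also rests on the projected counts, does not offer Table 1 as a threshold and gives no subgroup sizes, so no named subgroup is shown to fail.

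It can also be objected that 76% and 33% depend on an 80% power that the protocol never states. As a measure of the ratio alone they do not, because power and alpha cancel. As a distance from the stated 90% target, the right figures are 31% and 50% (5%) or 11% and 57% (2.5%).

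Finally, the pilot shares for 2016, "DPP4i (41.4 %), SU (35.4%) and SGLT2i (15.4"%), give 35.4/15.4 = 2.30, close to 7:3. A reader might infer that this is the source of the ratio. The protocol does not say so, and the point does not depend on it.

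**Conclusion.** The point holds. Table 1 is built on a 7:3 split that contradicts the cohort projected in two places of the same protocol, and its cells carry 80% power where text and caption both say 90%. For this cohort the 0.4/80% requirement is SU 837 + SGLT2i 935 at the power the cells carry, or about 1,120 + 1,251 at the stated 90% and 5%, against 1,471 + 630 printed.

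The claim of sufficiency for the overall SU versus SGLT2i comparison is not affected: power is 99.8% in the hardest cell at 5% two-sided. What is affected is the accuracy of the table and any minimum subgroup size read from it. The conclusion rests on the simple two-means formula with the effect multiplied by compliance, which is the form that reproduces the table. It makes no allowance for clustering or missing outcomes, and the subgroup shares assume the cohort's drug mix within each subgroup.

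**What to change.** Recompute Table 1 once at SU:SGLT2i = 6,000:6,700, with a single alpha and a single power that agree between text, caption and cells. State the ratio and the formula in the caption. Correcting the ratio without settling power and alpha would leave the table inconsistent with the text. Then express the subgroup sentence as the minimum share of the cohort that a subgroup needs to reach the stated power; at 0.4, 80% compliance and 90%/5% that is about 19%.

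The cost is one table, its caption and one sentence. No patients are added and no analysis changes. Compared with the printed table, the SGLT2i requirement rises and the SU requirement falls.

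### Table 1 is labelled 90% power (5% two-sided in the text, 2.5% in the caption), but its cells are 80%-power, 5% two-sided sample sizes at an unstated 7:3 split

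*Protocol*

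**What the plan says.** The protocol's sample size section (section 4, Objective 2) projects "approximately 25,700 (SU=6000, DPPi4=13,000, SGLT2i=6,700) patients". It takes as clinically relevant an "average between-treatment difference in the HbA1c change from baseline of 0.4% (e.g. from 8.0% to 7.6%) is of clinical significance", and on variability it says: "The assumed standard deviation of 2.4 is taken from a previous study of patients with T2DM recruited from CPRD". The error rates are set by the sentence "We require 90% power at the 5% (2-sided) level of statistical significance".

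It describes instrument strength twice. One sentence takes a base-case "level of non-compliance of 10%, but also consider scenarios with alternative levels". A later one sets base-case compliance at 80%, with 70% and 90% as alternatives, and these three levels are the column headings of Table 1.

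Table 1 gives SU and SGLT2i numbers for differences of 0.3, 0.4 and 0.5. Its first row reads "3416 1464 2615 1121 2066 886" (SU then SGLT2i, at 70%, 80% and 90% compliance). The caption describes the table as being for "magnitude of effect size at 90% power and 2.5% (2-sided) level of statistical significance". The section concludes that the anticipated sample is ample for the overall comparison, and then that the major subgroups can be estimated precisely enough. No allocation ratio is stated, and 80% power is not mentioned.

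**The concern.** The text and the caption give different two-sided significance levels for the same table, so at least one is wrong without any calculation. The printed numbers also look too small for 90% power with an SD of 2.4, and they have more than twice as many SU as SGLT2i patients, whereas the same section projects slightly fewer SU.

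Table 1 is the protocol's only quantitative power statement. A reader will take each cell as the number that gives 90% power and may compare subgroup sizes with it. If the cells deliver less, that benchmark is wrong.

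**Working it through.** **Inputs.** From the sample size text: SD 2.4; projected 6,000 SU and 6,700 SGLT2i; 90% power at 5% two-sided. From Table 1: differences d = 0.3, 0.4, 0.5; compliance c = 0.7, 0.8, 0.9; the printed pairs; 90% power at 2.5% two-sided (caption). Inferred, not stated: the effective difference is d × c, and the split is 7:3.

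**Step 1: the z-sum implied by the printed pairs.** z-sum = d × c / [2.4 × √(1/n_SU + 1/n_SGLT2i)]. This uses the printed numbers directly, so it does not depend on any assumed split.

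Base case: 0.4 × 0.8 / [2.4 × √(1/1471 + 1/630)] = 0.32 / 0.1143 = 2.800.

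**Step 2: the printed figures reproduced.** At 80% power and 5% two-sided, n_SGLT2i = (1.960 + 0.842)² × (2.4/(d × c))² × (1 + 3/7), and n_SU = 7/3 of that. Results are rounded to the nearest patient.

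| d, c | Printed SU/SGLT2i | Ratio | z-sum | 80%/5% formula at 7:3 |
|---|---|---|---|---|
| 0.3, 70% | 3416/1464 | 2.33 | 2.801 | 3417/1465 |
| 0.3, 80% | 2615/1121 | 2.33 | 2.801 | 2616/1121 |
| 0.3, 90% | 2066/886 | 2.33 | 2.801 | 2067/886 |
| 0.4, 70% | 1921/823 | 2.33 | 2.800 | 1922/824 |
| 0.4, 80% | 1471/630 | 2.33 | 2.800 | 1472/631 |
| 0.4, 90% | 1162/498 | 2.33 | 2.801 | 1163/498 |
| 0.5, 70% | 1230/527 | 2.33 | 2.801 | 1230/527 |
| 0.5, 80% | 941/403 | 2.33 | 2.800 | 942/404 |
| 0.5, 90% | 744/319 | 2.33 | 2.802 | 744/319 |

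Every cell is reproduced within one patient.

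**Step 3: compare with the labels.** The z-sum needed is:
- 80% at 5%: 1.960 + 0.842 = 2.802
- 90% at 5%: 1.960 + 1.282 = 3.242
- 90% at 2.5%: 2.241 + 1.282 = 3.523

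The power of the printed numbers is Φ(2.80 − 1.960) = 80% at 5%, and Φ(2.80 − 2.241) = 71% at 2.5%. To reach 90% with the printed numbers, the SD would have to be about 2.4 × 2.80/3.242 = 2.07 (5%) or 2.4 × 2.80/3.523 = 1.91 (2.5%).

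**Step 4: required numbers at 90% power, keeping 7:3.** The multipliers are (3.242/2.802)² = 1.34 at 5% and (3.523/2.802)² = 1.58 at 2.5%. From here on, numbers are rounded up.
- Base case: 1,971/845 (5%) or 2,328/998 (2.5%), against 1,471/630.
- Largest cell (0.3, 70%): 4,575/1,961 or 5,404/2,316, against 3,416/1,464.

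**Step 5: required numbers at 90% power, projected 6,000:6,700 split.** n_SU = (z-sum)² × (2.4/(d × c))² × (1 + 6000/6700), and n_SGLT2i = n_SU × 6700/6000.
- Base case: about 1,121/1,252 (total 2,373) at 5%, or 1,324/1,478 (total 2,802) at 2.5%, against 1,471/630 (total 2,101).
- Largest cell: about 2,602/2,905 or 3,073/3,432, against 3,416/1,464.

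In all nine scenarios, at both alphas, the printed SU number is above the requirement, and the printed SGLT2i number and total are below it.

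**Step 6: power of the projected cohort.** The standard error is 2.4 × √(1/6000 + 1/6700) = 0.0427. In the least favourable scenario, 0.3 × 0.7 / 0.0427 = 4.92. Power is Φ(4.92 − 1.960) = 99.8% at 5% and Φ(4.92 − 2.241) = 99.6% at 2.5%. All other scenarios are higher.

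**The case against.** The strongest reply is that nothing turns on the error. The study uses existing records, so Table 1 sets no recruitment target and only checks adequacy. Step 6 shows that the check passes under either alpha. This stands, and it is why the point calls for a restatement and not a redesign.

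A second reply is that the 7:3 split and the d × c scaling are inferred. That is true. However, step 1 takes the group sizes as printed, and one constant across nine cells leaves little doubt about the scaling. Reading the caption's 2.5% as a one-sided level would explain the alpha label, since 2.5% one-sided gives the same numbers as 5% two-sided. It would not explain the 90%.

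Stronger conclusions are tempting, but the documents do not support them:
- **Every required number is understated.** This is so only if 7:3 is kept. At the projected split, every SU number is overstated.
- **The SU group is nearly used up.** At 7:3 and 2.5%, the largest cell would take 5,404 of 6,000 SU patients (90%). At the projected split it takes about 3,073 (51%), less than the 57% that the printed 3,416 implies.
- **The subgroup claim fails.** That sentence rests on the projected cohort, cites no cell of Table 1 and gives no subgroup size. For illustration only, assume a subgroup holding a quarter of each group (1,500/1,675; standard error 0.0853). For 0.3 at 70% compliance the z-value is 0.21/0.0853 = 2.46, so power is 69% at 5% or 59% at 2.5%. For the base case it is 0.32/0.0853 = 3.75, so power is 96% or 93%. Adequacy therefore depends on the subgroup and the scenario, which the protocol does not specify.

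**Conclusion.** The point holds as a wrong power statement. Text and caption contradict each other on alpha, and the cells match neither: they give 80% power at 5% two-sided and about 71% at 2.5%. They are also built on a 7:3 split that the section's own projections do not support. The shortfall is a factor of 1.34 or 1.58 at the table's split. At the projected split the error changes direction by group: SU too high, SGLT2i and total too low.

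A reader might infer that the study is underpowered. It is not, for the overall SU versus SGLT2i comparison: simple power is at least 99.6% in every scenario. That figure uses a normal approximation, SD 2.4 and the protocol's compliance scaling, with no allowance for clustering or missing data. The point should be fixed, but it does not threaten the design. The practical risk is that someone uses the printed cells as a 90%-power benchmark for subgroups.

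**What to change.** Choose one two-sided alpha and state it in both the text and the caption. Then do one of the following:
- **Recompute** Table 1 at 90% power for that alpha with the projected 6,000:6,700 split, and state the split and the compliance scaling under the table. The base case becomes about 1,121/1,252 at 5% or 1,324/1,478 at 2.5%.
- **Relabel** the existing table as 80% power, 5% two-sided, 7:3 allocation, and change the sentence that requires 90% power to agree.

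The first is preferable because it also removes the mismatch in allocation. In either case, say that the overall sample remains sufficient and quote its power before clustering and missing data. Do not use the present cells to judge subgroups. While editing, reconcile the two base-case statements (10% non-compliance and 80% compliance).

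The cost is one recalculated or relabelled table and a few sentences. No extra patients are needed, and neither the design nor the analysis changes.

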We will extract all the required information on prescriptions by extending previous algorithms developed to identify antidiabetic regimens from CPRD, ⁷ to extract all the required information on concomitant medications. A major challenge is that for each drug, the definitions will be required to consistent with those applied to the United States Department of Veterans Affairs (VA) electronic medical record and Medicare Claims databases in building the original RAPIDS model. The study will therefore develop general codes to identify all the anti-diabetic, anti-hypertensives and lipid lowering drugs based on British National Formulary chapter and drug codes. We will use these codes to identify the second-line treatment, and extract the dose and estimated dates of initiation and cessation for each treatment. To provide measures of long-term effectiveness requires that information on all relevant prescriptions is extracted for the maximum follow-up time for each patient.

Outcomes

From the onset of second-line treatment until the maximum duration of follow-up, the study will extract information from the CPRD on biomarkers (HbA1c, HDL, LDL and total cholesterol, triglycerides, SBP, DBP, eGFR, body weight, and BMI). Follow-up for all patients will be censored at the date of death, transfer out of the practice or end of data collection, whichever is earliest. We will report the time to cessation of first-line intensification. From the HES-linked data, we will use ICD10 diagnostic codes as primary or secondary diagnoses, to identify inpatient hospital admissions associated with T2DM including hypoglycaemia, MI, CHF, unstable angina, stroke, ESRD, and lower limb amputation. We will extract information on mortality, including date of death, from linkage to ONS mortality data.

Missing data in the CPRD-HES linked cohort

The main potential issues are missing values for baseline case-mix variables and biomarkers at particular time-points. Drawing on the precedent study we expect <5% of patients will have missing values for baseline variables such as BMI, with the exception of ethnicity (c10%), for which missing data will be minimised by using HES admission data from linked episodes.

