For the main comparative effectiveness analysis (obj 2) we will handle all missing baseline and longitudinal outcome data by multiple imputation³² with chained equations.³³ This approach assumes data are missing at random. The imputation of each long36itudinal outcome at a given time point will use all relevant information, including measurements of the same outcome at other time points. This use of auxiliary information can help the study recover more accurate estimates of the unknown outcome values.³⁴ This will help ensure our study population is comparable across the second-line treatments at each time point. Partially observed covariates and outcomes^{35 36} will be multiple imputed by predictive mean matching with 10 donors, producing five imputed datasets. The number of imputations will be driven by the need to balance computational time with improved inference from increasing the number of imputations (see supplementary methods for further details). The imputation models developed for each covariate will be congenial with the form of outcome³⁷ (continuous or time to event). For the time-to-event endpoints, we will assume that there are no missing outcome data. All imputation models will be stratified by second line treatment (DPP-4 inhibitors, SGLT-2 inhibitors, sulfonylureas) and by whether the individual died or was censored before the relevant study end date.

[figure not shown]
Instrumental variable

Our proposed IV design follows research in pharmaco-epidemiology² that uses provider preference as an instrument for treatment prescribed. The IV will be the prescribing history in each CCG. This will be defined as the proportion of relevant prescriptions within the CCG for each first-stage treatment intensification in the last complete calendar year prior to the treatment intensification of the patient currently under consideration.

The key assumptions

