We will describe the baseline characteristics of the 'effectiveness' cohort, and the second-line treatment pathways. We will evaluate the relative effectiveness of each second-line treatment strategy incorporating the subsequent treatments that patients receive in current practice. This aspect of the study will be designed according to the target trial framework.⁴¹ In brief, a target trial is a hypothetical RCT for assessing comparative effectiveness from observational data which requires the definition of the main elements of a trial's protocol, including eligibility criteria and the respective treatment strategies. We will apply target trial principles⁴¹ to primary care data in England between 2015-2021 from the CPRD to identify people with T2DM who had similar prognosis prior to initiating any of the three second-line antidiabetic drug treatments under comparison.

Workshop

We will convene a design workshop to inform the proposed analysis. The panel of health care professionals and PPI representatives will advise on: the definition of personalisation; the choice of subgroup variables, building on those identified in the literature review; the communication of the risks and benefits of the alternative treatments; and the prioritisation of the different outcome measures. The clinical panelists will include diabetologists, GPs and practice nurses involved in care for people with T2DM. The majority of the PPI panellists will be people with T2DM who have experienced second-line treatment. Diabetes UK and local PPI panels convened by the co-applicants have agreed to support the study and participate in the workshops (see PPI section for full details).

Outcomes

The primary outcome will be the absolute change in HbA1c (mmol/mol) between baseline and 1-year following each second-line treatment prescription (HbA1c at 1-year – HbA1c at baseline). Treatment groups will be compared according to the mean change in HbA1c. We will use the measurement closest in time to the 1-year follow-up timepoint and allow for measures within ±90 days, otherwise the measure will be designated as missing.

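### The one missing-data sensitivity analysis the protocol names, complete records, does not explore a 1-year HbA1c that is missing not at random

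*Protocol*

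**What the plan says.** The primary outcome of Objective 2 is change in HbA1c from baseline to one year. Under Objective 2, Outcomes, the value nearest to one year is used; the rule is to "allow for measures within ±90 days, otherwise the measure will be designated as missing".

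Under Missing data in the CPRD-HES linked cohort, for the main comparative effectiveness analysis, "we will handle all missing baseline and longitudinal outcome data by multiple imputation". The next sentence states the assumption: "This approach assumes data are missing at random". The imputation draws on auxiliary data, "including measurements of the same outcome at other time points", and is stratified by drug and "by whether the individual died or was censored before the relevant study end date". Baseline gaps are expected in under 5% of patients, with ethnicity at about 10%. No corresponding percentage is given for 1-year HbA1c.

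Under Objective 2, Sensitivity analyses, the protocol says: "We will consider different assumptions about missingness patterns, for example by undertaking complete records analysis". The reference attached to that sentence (number 47) is a methods paper whose title concerns covariates, not outcomes, that are missing not at random. No delta-adjusted, pattern-mixture, reference-based or selection-model analysis is named. In section 11 the mitigation offered for missing biomarkers is multiple imputation.

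**The concern.** HbA1c is recorded when routine care chooses to test. A plausible failure is that people are tested, or not tested, around one year for reasons tied to the value that would have been found, beyond what their other measurements show. The instrument addresses unmeasured confounding of drug choice; it does not repair outcome-dependent missingness.

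The sensitivity sentence announces a change of missingness assumption, but its only example does not move the outcome assumption towards MNAR. For covariates, complete records can tolerate some MNAR patterns, but few covariate values are expected to be missing. The more exposed variable is the primary outcome, which Objectives 3 and 4 also use. A reader who sees imputation and complete records agree could take this as robustness to non-random testing, which the comparison cannot show.

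**Working it through.** **1. What each analysis assumes about a missing 1-year HbA1c.** Write Y for the 1-year value, X for the terms in the outcome model (drug, covariates, first-stage residuals), A for the auxiliary data in the imputation (HbA1c at other times, death or censoring stratum), and R for being observed.

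- Imputation: R independent of Y given X and A.
- Complete records: R independent of Y given X alone.

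The second is in practice the stricter form of MAR. Neither allows R to depend on Y itself once the conditioning set is fixed, so moving from one to the other does not explore MNAR.

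**2. Illustration by simulation.** The inputs are assumptions, not protocol figures: 200,000 patients in two equal-probability groups; Y = -0.4 x group + 0.5 x baseline + normal error (SD 2.0); later value = 0.5Y + normal error (SD 1.7). Missingness follows a logistic model with linear predictor -1 + 0.5 x group, plus 0.5 x baseline (row 1), 0.4 x later value in one group (row 2), or 0.3 x Y in one group (row 3). Imputation is by group with normal draws, five datasets and no instrumental-variable step.

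| Missingness depends on | Missing | Full data | Complete records | Imputation with later value |
|---|---|---|---|---|
| Baseline (MAR) | 33.1% | -0.391 | -0.386 | -0.381 |
| Later value (MAR for imputation only) | 32.2% | -0.395 | -0.662 | -0.399 |
| Y itself, one group (MNAR) | 31.7% | -0.402 | -0.797 | -0.705 |

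In the MNAR row both methods err in the same direction: complete records by -0.797 + 0.402 = -0.395, imputation by -0.705 + 0.402 = -0.303. They differ from each other by 0.797 - 0.705 = 0.092. In the second row, where imputation is right to within 0.004, they differ by 0.662 - 0.399 = 0.263. The gap is thus larger when imputation is sound than when it is badly biased. These sizes come from the chosen parameters and are not forecasts for this study.

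**3. Possible size in this study.** With missing fractions m1 and m0, and unseen values departing from the MAR prediction by d1 and d0, the contrast moves by m1 x d1 - m0 x d0. This is approximate under 2SRI. The yardstick is the 0.4% difference that the sample size section treats as clinically significant. The missing fractions are assumed.

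- Shift of 0.4% in one drug only, 20% missing: 0.20 x 0.4 = 0.08%, which is 20% of the 0.4% difference.
- The same shift, 40% missing: 0.40 x 0.4 = 0.16%, which is 40% of it.
- The same 0.4% shift in both drugs, 5-point gap in missingness: 0.05 x 0.4 = 0.02%, which is 5% of it.
- One-sided shift needed to move the contrast by the full 0.4%: 0.4/0.10 = 4.0%, 0.4/0.20 = 2.0%, 0.4/0.30 = 1.33% and 0.4/0.40 = 1.0% at 10, 20, 30 and 40% missing.

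**4. Units.** The primary outcome is in mmol/mol. A difference of 0.4% is 0.4 x 10.93 = 4.4 mmol/mol.

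**The case against.** The strongest reply is that this is detail for an analysis plan. Only the protocol is at hand, its timetable schedules final analysis plans at month 9, and the missing-data section points to supplementary methods that are not shown (in a sentence about the number of imputations). The sensitivity sentence also gives complete records only as an example, so the list is open. This stands to the extent that nobody can say an MNAR analysis is absent from the whole study. It does not remove the point that the one example fixed here does not do, for the primary outcome, what the sentence announces. A plan faithful to that sentence could stop there.

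Second, a reader might infer that the two analyses rest on the same assumption, or that MAR will go untested. The protocol supports neither reading. Imputation conditions on HbA1c at other times and on death or censoring, so the assumption is varied, only not towards MNAR. And MAR cannot be tested from observed data by any method; a delta analysis explores departures and does not test it.

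Third, testing that depends on control already visible at baseline or at other recorded times is compatible with MAR and enters the imputation. That also stands: only dependence on the unseen 1-year value beyond those data is at issue.

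Fourth, the larger magnitudes need a shift confined to one drug and equal to the whole clinically significant difference. Nothing in the protocol supports or excludes so lopsided a shift, so they are illustrations.

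**Conclusion.** The point holds as a low-cost improvement. For the primary outcome, the only missing-data sensitivity analysis named is a stricter form of MAR than the main analysis, so it leaves MNAR unexplored. Comparing it with imputation cannot reliably show or rule out outcome-dependent testing.

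The size is unknown because the missing fraction is not stated. Under the assumed fractions, a one-drug shift of 0.4% matters moderately against the 0.4% yardstick (0.08-0.16%), and a common shift hardly matters (about 0.02%).

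A reader might go further and conclude that the drug contrasts are biased, or that complete records could never show any sign of trouble. The documents do not support either. No evidence of outcome-dependent testing is given, and in the MNAR simulation the two methods did differ somewhat, though not in a way that could be attributed to MNAR.

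**What to change.** In Objective 2, Sensitivity analyses, keep complete records and describe it as the check on missing covariates. Add a delta-adjusted (pattern-mixture) analysis of the primary outcome: add a pre-set delta to the imputed 1-year HbA1c values separately by drug, for example over -0.4% to +0.4% (about -4.4 to +4.4 mmol/mol). Rerun the 2SRI on the shifted datasets and report, for each pairwise contrast, the between-drug delta at which the conclusion changes, or that it does not change within the grid. Report the observed missing fraction by drug beside it, since that fixes how far a given delta can move the result. Set the grid before results are seen.

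The imputations are already stratified by drug, so the change fits the existing structure and needs no new data. The cost is computing: the protocol limits itself to five imputations partly for time, and it bootstraps all standard errors. Five delta values crossed over three drugs would be 5 x 5 x 5 = 125 reruns; shifting one drug at a time over the four non-zero values would be 3 x 4 = 12. The other cost is that some conclusions may have to be stated as holding only within a range of delta.
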